3.2 SECONDARY ENDPOINTS

Immunogenicity:

- Geometric mean and median titers of type 2 polio neutralizing antibodies Day 0 and 28 days after the second dose of nOPV2 when administered 1, 2, or 4 weeks apart.
- Cumulative fold-rise (from Day 0) in titers of type 2 polio neutralizing antibodies 28 days after the second dose of nOPV2 when administered 1, 2, or 4 weeks apart. Cumulative fold-rise will be computed relative to the expected level of maternally-derived antibody titers in accordance with the seroconversion definition.
- Fold-rise (from post-dose-1 level) in titers of type 2 polio neutralizing antibodies 28 days after the second dose of nOPV2 when administered 1, 2, or 4 weeks after dose-1. This fold-rise will be computed from the level attained following the first dose, with the pre-dose-2 serum sample.
- Seroprotection rate to poliovirus type 2, at Day 0 and 28 days after the second dose of nOPV2 when administered 1, 2, or 4 weeks apart.
Seroprotection rate is defined as the percentage of subjects with type 2-specific antibody titers $\geq 1:8$.
- Geometric mean and median titers of type 2 polio neutralizing antibodies 1, 2, and 4 weeks after 1 dose of nOPV2.
- Fold-rise in titers of type 2 polio neutralizing antibodies 1, 2, and 4 weeks after 1 dose of nOPV2. This fold-rise will be computed relative to the expected level of maternally-derived antibody titers in accordance with the seroconversion definition.
- Seroconversion rate 1, 2, and 4 weeks after 1 dose of nOPV2.
- Seroprotection rate 1, 2, and 4 weeks after 1 dose of nOPV2.

Safety:

- Incidence of SAEs and IMEs as of the informed consent signature date and throughout the study period in all groups by severity and causal association.
- Incidence of mild, moderate and severe solicited AEs (fever, vomiting, abnormal crying, drowsiness, loss of appetite, diarrhea and irritability) for 7 days after each dose of study vaccine in all groups.
- Incidence of mild, moderate and severe unsolicited AEs for 28 days after each dose of study vaccine by causal association in all groups.

3.3 EXPLORATORY ENDPOINTS

- Geometric mean and median titers of type 2 polio neutralizing antibodies at Day 0 and 28 days after the second dose of nOPV2 when administered 1 or 2 weeks apart.

14 August 2021 (Version 1.0)

- Cumulative fold-rise (from Day 0) in titers of type 2 polio neutralizing antibodies 28 days after the second dose of nOPV2 when administered 1 or 2 weeks apart.
- Seroprotection rate to poliovirus type 2, at Day 0 and 28 days after the second dose of nOPV2 when administered 1 or 2 weeks apart.
- Seroconversion rate to poliovirus type 2, 28 days after the second dose of nOPV2 when administered 1 or 2 weeks apart.

4. STUDY DESIGN

4.1 OVERVIEW OF THE STUDY DESIGN

This will be a multicenter, randomized, controlled, open-label, parallel-group Phase III study in healthy infants aged 6 to 8 weeks who have never been vaccinated against poliomyelitis.

Approximately 900 infants will be included in the study and randomized with a 1:1:1 ratio to the following treatment groups:

- Group A: approximately 300 subjects to receive 2 doses of nOPV2 administered 1 week apart, at Day 0 and Day 7;
- Group B: approximately 300 subjects to receive 2 doses of nOPV2 administered 2 weeks apart, at Day 0 and Day 14;
- Group C (control group): approximately 300 subjects to receive 2 doses of nOPV2 administered 4 weeks apart, at Day 0 and Day 28.

A total of 4 on-site visits are planned. Approximately 7 days after each administration of study vaccine, a phone call or on-site visit will be performed to monitor subjects' safety and review with the subject's parent(s)/guardian(s) any solicited AEs reported in the electronic diary card. All subjects will have a safety follow-up phone call 6 months after the last dose of study vaccine.

All infants will receive concomitant routine vaccinations included in the National Immunization Program (NIP) in the Dominican Republic, as follows:

- Group A: pentavalent vaccine (diphtheria, tetanus, whole-cell pertussis, hepatitis B, Haemophilus influenzae type b, [DTPw-HB-Hib]) and pneumococcal conjugate vaccine (PCV) at 6-8 weeks of age, rotavirus vaccine at 8-10 weeks of age and the first dose of inactivated poliovirus vaccine (IPV) at 11-13 weeks of age;
- Group B: pentavalent vaccine (DTPw-HB-Hib) and PCV at 6-8 weeks of age, rotavirus vaccine at 9-11 weeks of age and the first dose of IPV at 12-14 weeks of age;
- Group C: pentavalent vaccine (DTPw-HB-Hib) and PCV at 6-8 weeks of age, rotavirus vaccine at 11-13 weeks of age and the first dose of IPV at 14-16 weeks of age.

The total study duration will be approximately 8 to 9 months. Each infant will participate for a duration of up to approximately 7 months, which includes a 6-month follow-up period after last vaccine administration to gather additional safety data on the nOPV2 vaccine.

A Data and Safety Monitoring Board (DSMB) will monitor the safety aspects of this study.

Assign Data Management and Biostatistics will be responsible for the generation of randomization codes and files.

4.2 DISCUSSION OF STUDY DESIGN

Subjects will be randomized in a 1:1:1 ratio to increase the likelihood that known and unknown subject attributes (e.g., demographic and baseline characteristics) are evenly balanced across groups.

The study will be conducted in an open-label manner. The evaluation of the primary immunogenicity endpoint is not expected to be biased given its objective nature.

Laboratory personnel will be blinded to group until such time as the neutralizing antibody assays are complete, and samples from all groups will be randomized for concurrent testing.

Subjects' safety will be closely monitored throughout the study during the on-site visits and the phone calls. Phone calls or on-site visits 7 days after each administration of nOPV2 will enable to review with the subject's parent(s)/guardian(s) any solicited AEs reported in the electronic diary. A dedicated phone visit 6 months after the last dose of study vaccine will enable the collection of long-term safety data. In addition, a DSMB will monitor the safety aspects of this study enrolling a very young population of children.

In addition to the vaccination with nOPV2, infants will receive the DTPw-HB-Hib, PCV and rotavirus vaccine as recommended by the NIP of the Dominican Republic. To avoid the interference of any additional poliovirus vaccines with nOPV2 immunogenicity assessments, it is planned to administer IPV 4 weeks after the second dose of nOPV2.

5. SELECTION OF STUDY POPULATION

For details on the sample size calculation, please refer to Section 10.2.

5.1 INCLUSION CRITERIA

1. Infants aged 6 to 8 weeks with birth weight >2,500 g.
2. Healthy infants without obvious medical conditions like immunodeficiency diseases, severe congenital malformations, severe neurological diseases or any other disease that require high doses of corticosteroids or immunotherapies that preclude the subject from participating in the study as established by the medical history and physical examination.
3. Written informed consent obtained from 1 or 2 parent(s) or legal guardian(s) as per country regulations..

5.2 EXCLUSION CRITERIA

Subjects meeting any of the following criteria are excluded from participation in this study:

1. Infants who have received previous vaccination against poliomyelitis.
2. Infants with anyone under 5 years of age in their household (living in the same house or apartment unit) who does not have the complete “age appropriate” vaccination status with respect to poliovirus vaccines at the time of study vaccine administration according to the Dominican Republic NIP.
3. Infants having a member of their household (living in the same house or apartment unit) who is under 6 months of age at the moment of study vaccine administration.
4. Infants having a member of their household (living in the same house or apartment unit) who has received OPV in the previous 3 months before study vaccine administration.
5. Any confirmed or suspected immunosuppressive or known immunodeficient condition including human immunodeficiency virus infection in the potential participant or any member of the subject’s household.
6. Family history of congenital or hereditary immunodeficiency.
7. Major congenital defects or serious uncontrolled chronic illness (neurologic, pulmonary, gastrointestinal, hepatic, renal, or endocrine).
8. Known allergy to any component of the study vaccine or to any antibiotics that share molecular composition with the nOPV2 vaccine.

9. Administration of immunoglobulins and/or any blood products since birth or planned administration during the study period.
10. Acute severe febrile illness on the day of vaccination deemed by the Investigator to be a contraindication for vaccination (the child can be included at a later time if within age window and all inclusion criteria are met.).
11. Subject who, in the opinion of the Investigator, is unlikely to comply with the protocol or is inappropriate to be included in the study for the safety or the benefit-risk ratio of the subject.
12. Infants from multiple births or born prematurely (< 37 weeks of gestation).

5.3 CRITERIA FOR ELIMINATION FROM THE PER-PROTOCOL POPULATION

A review of protocol deviations, including, among others, vaccinations occurring out of window, administration of other polio vaccines, and OPV administration to household members, will be conducted prior to database lock based on predefined criteria. Subjects with major protocol deviations detected via monitoring or automated database search which are deemed likely to interfere with the assessment of immunogenicity will be removed from the per-protocol population at the time of occurrence of the first such deviation. Subjects receiving other vaccinations not per protocol (non-study polio vaccinations, or non-NIP vaccinations) will contribute safety data to the Total Vaccinated Population (TVP) prior to administration of the non-study/non-NIP vaccination, although they will still be followed for safety for the remaining study duration, with data presented in separate summaries. They will not receive further study vaccine doses.

5.4 CONTRAINDICATIONS TO FURTHER VACCINATION

The following AEs constitute absolute contraindications to further administration of the study vaccine:

- SAE, severe adverse event (grade 3) or IME after vaccination considered to be consistent with a causal association to the study vaccine.
- Known hypersensitivity to any component of the vaccine or any antibiotic or severe reaction following previous administration of the vaccine.
- Acute severe febrile illness on the day of vaccination deemed by the Investigator to be a contraindication for vaccination.
- Diagnosis between 2 visits of any of the following medical conditions:
 - o Uncontrolled severe chronic disease (see above under exclusions).
 - o Coagulopathy.
 - o Congenital or acquired immunodeficiency syndrome.
 - o Acute flaccid paralysis (to be investigated as a SAE).

If any of these AEs occur during the study, the subject should not receive the second dose of vaccine but may continue other study procedures at the discretion of the Investigator. The subject will be followed until resolution of the event and to determine the immune response.

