All AEs will be summarized by group, type, by post-vaccination timepoint and overall (regardless of timing of onset), by severity and occurrence in relation to vaccination, and overall, separately for solicited and unsolicited AEs. Determination of causal association of unsolicited AEs, SAEs and IMEs to the study

vaccines will be assigned using the individual causality assessment algorithm published by the World Health Organization (WHO).

Separate tables and listings will be created for subjects who died, discontinued the study vaccine due to an AE, or experienced an SAE. Summaries, listings, and narratives may be provided, as appropriate.

Unsolicited AEs occurring within 28 days of any vaccine administration will be summarized, as will any data obtained on SAEs or IMEs reported during the safety follow-up.

Data Safety Monitoring Board:

A DSMB will monitor the benefit-risk and data integrity of this study. The composition and functioning of the DSMB will be documented in the DSMB charter.

TIME AND EVENTS SCHEDULE

Table 1 Group A: Administration of 2 doses of nOPV2, 1 week apart

Visit	Visit 1	Visit 2	Visit 3	Visit 4	Visit 5
Time of Visit/Phone call (days)	D 0	D 7 (+ 2 days)	D 14 (+ 2 days)	D 35 (+ 2 days)	D 187^a (+ 7 days)
Visit Window					
On-site/phone call	On-site	On-site	On-site	On-site	Phone-call
Informed consent ^b	X				
In-/exclusion criteria	X				
Medical history/concomitant diseases	X				
Medication/vaccination history	X				
Demographic data	X				
Physical examination	X	X			
Randomization	X				
Serum sample for polio antibody measurement ^c	X	X		X	
Administration of nOPV2 ^d	X	X			
Vaccination according to the NIP ^e	X		X	X	
Solicited adverse events (diary) ^f	X	X	X		
Unsolicited adverse events ^g	X	X	X	X	
Concomitant therapies ^h	X	X	X	X	X
Adverse events ^h	X	X	X	X	X

D: day; NIP: national immunization program

- a. In case of early termination the subjects' parents will be contacted by phone within 14 days after discontinuation for assessments as outlined on Day 187.
- b. No study-related assessment is to be carried out before signing the informed consent form.
- c. Serum sample for immunogenicity assessments is to be collected before administration of nOPV2 and IPV.
- d. Subjects will be kept under medical supervision for at least 30 min after vaccination.
- e. Infants participating in the study should receive vaccines as recommended by the NIP. They will receive:

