8.3 SAFETY EVALUATIONS

The safety assessment in this study will be based on AEs.

Adverse events will be monitored continuously from the time of informed consent signature until Day 187 (Group A), Day 194 (Group B) or Day 208 (Group C) (180 + 7 days after the last administration of the study vaccine). At regular intervals during the study, at the on-site visits and over the phone, parents will be asked non-leading questions to determine the occurrence of any AEs.

For detailed definitions and reporting procedures of AEs, see Section 11.

Solicited AEs will be recorded by the subjects' parent(s)/guardian(s) for 7 days following each dose of study vaccine using a diary card. These will be reviewed by the Investigator during the phone calls or on-site visits that will be scheduled with the subject's parent(s)/guardian(s) 7 days after each dose. In addition, unsolicited AEs will be collected during regular study phone calls and on-site visits for 28 days after each vaccination. Any SAEs and IMEs will be collected from the date of the informed consent signature throughout the study.

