9.2 REMOVAL OF SUBJECTS FROM STUDY OR INVESTIGATIONAL PRODUCT

9.2.1 Removal from Study

Parents(s)/guardian(s) have the right to withdraw subjects from the study at any time for any reason, including personal reasons. A subject can be withdrawn without giving a reason. The Investigator should however try to find out why a subject is withdrawn from the study and document the reason for withdrawal in the source documents and on the eCRF.

Subjects **may** be withdrawn from the study in the event of:

- A severe AE or a SAE;
- Difficulties in obtaining blood or other samples;
- Failure of the subject and/or subject's parent(s)/guardian(s) to comply with the protocol requirements or to cooperate with the Investigator.

Subjects **must** be withdrawn from the study in the event of:

- Withdrawal of consent by parent(s)/guardian(s);
- For safety reasons, if, in the Investigator's opinion, in the best interest of the subject.

In the event of a subject being withdrawn from the study, the monitor and Sponsor should be informed: in the event of withdrawal due to an SAE (for details on AE reporting see Section 11), the Sponsor should be notified within 24 hours; in the event of withdrawal for other reasons, the Sponsor should be notified within 2 days from the event.

If there is a medical reason for withdrawal, the subject will remain under the supervision of the Investigator until satisfactory health has returned.

Subjects who are withdrawn from the study prior to completion of the scheduled study procedures for any reason (e.g. AE, withdrawal of consent) should be invited to complete

the assessments as much as possible: as long as the subjects' parent(s)/guardian(s) consents, all relevant assessments of the day on which the subject withdrew from the study should be completed, at least those related to safety. In case of an AE, the appropriate follow-up will be done.

Subjects who are withdrawn from the study will not be replaced.

9.2.2 *Removal from Investigational Product*

Removal from investigational product administration concerns subjects who do not receive a complete study vaccination schedule as planned per protocol. A subject who is withdrawn from further study vaccine administration need not necessarily be withdrawn from the study as further study procedures or follow-up may be performed (safety or immunogenicity) if planned in the study protocol.

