Information pertaining to premature discontinuation of the study vaccine will be documented in the eCRF. The Investigator will document whether the decision to discontinue further vaccination was made by the subjects' parent(s)/guardian(s) or the Investigator, and which of the following possible reasons was responsible for withdrawal:

- SAE/IME.
- AE.
- Other (specify).

10. **STATISTICAL METHODS**

10.1 **STATISTICAL ANALYSIS**

All statistical analyses will be performed by Assign Data Management and Biostatistics GmbH, [name] using SAS® software (SAS Institute Inc., Cary, NC, USA) under the supervision and responsibility of the Sponsor.

This document describes the basic elements of the statistical analysis to be performed. All statistical methods shall be detailed in a Statistical Analysis Plan (SAP) that will be finalized before database lock.

Unless otherwise specified, descriptive statistics include mean, standard deviation, median, maximum, minimum, and range for continuous variables and the number and percentage in each group for categorical variables.

Unless specified otherwise in the SAP, statistical tests and CIs will be computed using a two-sided 5% significance level. Exact (Clopper-Pearson) CIs will be used for univariate summaries of dichotomous variables, and Miettinen-Nurminen score-based CIs will be used for rate differences.

10.1.1 ***Study Populations***

The following populations will be considered for analysis:

- The Enrolled Population is defined as all subjects for whom informed consent is provided, regardless of the subject's randomization and vaccination status.
- The TVP is defined as all subjects who received at least 1 dose of study vaccine.
- The Reactogenicity Population is defined separately for each dose (dose 1 and dose 2) as those subjects who received the respective dose and who completed the diary card.

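### Household immunodeficiency bars entry under exclusion 5, but section 5.4 carries only the infant's own immunodeficiency forward to dose 2, and no household question is scheduled before the second live dose

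*Combined protocol and SAP*

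**What the plan says.** Section 5.2, exclusion 5, rules out an infant with "Any confirmed or suspected immunosuppressive or known immunodeficient condition including human immunodeficiency virus infection in the potential participant or any member of the" infant's household. Exclusion 6 adds a family history of congenital or hereditary immunodeficiency.

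In the Time and Events Schedules (Tables 1, 2 and 3), the row "In-/exclusion criteria" is marked once, at Day 0. The rows for medical history and for medication and vaccination history are also marked only at Day 0. The dose-2 visit falls on D 7 in Group A, D 14 in Group B and D 28 in Group C. It includes a physical examination, a serum sample, adverse event collection and concomitant therapies.

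Section 5.4 decides who may receive dose 2. Its list opens with "The following AEs constitute absolute contraindications to further administration of the study vaccine". Among the diagnoses made between visits it names "Congenital or acquired immunodeficiency syndrome". If a listed event occurs, "the subject should not receive the second dose of vaccine but may continue other study procedures at the discretion of the Investigator". No household member is mentioned.

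**The concern.** Section 1.3.1 states that vaccine virus may be excreted for several weeks and can pass to contacts. It adds that, where population immunity is low, a close contact may very rarely be at risk of paralysis caused by the vaccine. Exclusion 5 gives no rationale, but with that risk text beside it the household clause reads most naturally as protection for contacts.

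On that reading, the protocol treats an affected household member as reason enough to withhold the first live dose. It is silent if such a member is recognised, or first suspected, between the doses. It gives no reason for handling the two doses differently. At stake is the safety of a household contact who is not a trial participant. The statistical result is not at stake.

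**Working it through.** This is mainly a comparison of texts. The arithmetic only bounds the statistical side.

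**1. Which entry criteria does section 5.4 repeat for dose 2?**

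| Entry criterion (5.2) | Counterpart in 5.4 |
|---|---|
| 5, infant's own immune condition | Yes, as a diagnosis between visits |
| 5, household member's immune condition | None |
| 7, serious uncontrolled chronic illness | Yes, with a pointer back to the exclusions |
| 8, allergy to vaccine components or antibiotics | Yes, as hypersensitivity |
| 10, acute severe febrile illness | Yes, almost unchanged |

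So 5.4 is where entry criteria are carried forward, and the household half of exclusion 5 is not among them. The immunodeficiency bullet does not say in whom the diagnosis is made. However, the list is headed as adverse events, section 11.1.1 ties these to what follows immunization, and the stated consequence concerns the subject. A condition in a parent or sibling does not fit.

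**2. Does another section close the gap before dose 2?**

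- Section 8.3: "parents will be asked non-leading questions to determine the occurrence of any AEs". These questions concern adverse events.
- Section 9.2.1: mandatory withdrawal on safety grounds applies when it is "in the best interest of the subject". A contact's interest is not covered.
- Section 9.2.2: a free-text category lets a site record another reason for stopping vaccination. It does not prompt anyone to ask.
- Section 5.3: household OPV is reviewed before database lock to decide per-protocol membership. It is a different question, asked too late to affect dosing.
- Exclusions 2 to 4 are tied to the time of study vaccine administration and could be read as applying at each dose. Exclusion 5 has no such wording.

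None of these prompts a household question before dose 2.

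**3. The window between doses.** Taking 300 infants per group and the scheduled days:

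- Group A: 300 × 7 = 2,100 household-days
- Group B: 300 × 14 = 4,200
- Group C: 300 × 28 = 8,400
- Total: 14,700

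At a constant rate of new recognition, Group C would have 28/7 = 4 times as many cases as Group A. The documents give no such rate, so no expected count follows.

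**4. Effect on power.** Inputs from section 10.2: 85% seroconversion in each group, margin 10 points, two-sided 5%, 90% power, 270 evaluable per group.

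- Reproducing the plan: n = (1.960 + 1.282)² × 2 × 0.85 × 0.15 / 0.10² ≈ 268 per group, against 270 stated.
- Power = Φ(0.10/SE − 1.960), with SE = √[0.85 × 0.15 × (1/n₁ + 1/n₂)].
- 270 v 270: SE = 0.03073, power = Φ(1.294) = 90.2%.
- 270 v 268, assuming for illustration that two Group C infants are withheld dose 2: SE = 0.03079, power = Φ(1.288) = 90.1%.

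The same rate would give 2 × 14/28 = 1 infant in Group B and 2 × 7/28 = 0.5 in Group A, or 3.5 of 900 in all.

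**The case against.** The strongest reply is that little risk is left. Exclusion 5 already covers suspected as well as confirmed immunosuppressive conditions, and exclusion 6 covers family history. What remains is a condition that escaped both at Day 0 and came to light within 7, 14 or 28 days. By then the household may already have been exposed to dose-1 virus. Section 1.3.1 ties the contact risk to populations with low immunity, calls it very rare, and does not mention immunodeficient contacts. It also reports improved genetic stability of nOPV2 and anticipates no increase in vaccine-associated paralysis. An investigator who learned of such a household member could stop vaccination anyway.

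All of this stands, and it sets the priority low. It does not supply the missing instruction: discretion helps only if someone asks, and nothing in the protocol prompts the question.

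A reader might infer that nothing is checked before dose 2. The documents do not support that. The infant is examined, adverse events are collected, and 5.4 covers the infant's own diagnoses and acute illness. Only the household question is absent.

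**Conclusion.** The gap is real and narrow. Section 5.4 does not extend the household part of exclusion 5 to dose 2, and Tables 1-3 schedule no question that would bring a new household condition to light. A small contact-safety amendment is worth making, at low priority.

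The conclusion rests on two readings: that 5.4 concerns the infant, which its framing supports, and that exclusion 5 is meant to protect contacts, which is plausible but not stated. The number of infants affected will be very small and cannot be estimated from the documents. Nor do they allow any estimate of the harm avoided; withholding dose 2 lowers exposure but cannot undo shedding from dose 1.

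It would be tempting to argue that the omission weakens the non-inferiority comparison. It does not. The primary endpoint, the margin and the sample size are unaffected, and the illustrative loss of two Group C infants costs about 0.1 percentage point of power.

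**What to change.** 1. Add one line to section 5.4: a newly recognised or suspected immunodeficient or immunosuppressive condition in a household member bars dose 2. The infant may continue other procedures under the existing 5.4 wording.
2. Add one row to Tables 1-3: a household question asked before dosing at the existing dose-2 visit (Group A Visit 2, D 7; Group B Visit 3, D 14; Group C Visit 3, D 28).

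The cost is one sentence, one table row and up to 900 short answers at visits already held on site. No new discontinuation code is needed, because section 9.2.2 already has a free-text category. The downside is that a very small number of infants would miss dose 2 and leave the post-dose-2 per-protocol analysis, slightly more of them in Group C because of its longer interval. Under section 10.1.1 the per-protocol population is adapted by time point, so their data up to that point could still be used.

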- The Per-Protocol (PP) Population consists of all eligible study participants who are in the TVP, who provided an evaluable pre-vaccination serum sample, and who received all of the immunizations at the interval scheduled for the group to which they were allocated and excludes those subjects who received any therapy that could significantly affect the subject's immune status and those subjects who met criteria outlined in Section 5.3. The PP Population will be adapted by time point to allow subjects to contribute data to PP analyses until such time as they become disqualified. All deviations and violations occurring in the study will be reviewed prior to database lock and classified as either minor or major.

Unless specified otherwise, the TVP will be used for safety analysis and analysis of demographics. The Reactogenicity Population will be used to summarize incidence of solicited events. Immunogenicity analyses will be primarily conducted in the PP Population.

10.1.2 *Analysis Sequence*

A final analysis of immunogenicity outcomes will be conducted upon completion of assays and reconciliation of data, which may be in advance of the completion of safety follow-up. This will include an analysis of baseline characteristics and disposition. Safety data will be described upon completion of the study, including all safety follow-up.

10.1.3 *Initial Characteristics Data of the Subject Sample*

Descriptive statistics will be provided per group for demographic (e.g., age, weight, race, gender) and other initial subject characteristics (e.g., medical and surgical history, concomitant diseases). Demographics will be compared using Chi-squared and Fisher's exact test for categorical variables, and Kruskal-Wallis and pairwise Wilcoxon test comparisons for continuous variables.

Prior and ongoing medical history will be coded with the Medical Dictionary for Regulatory Activities (MedDRA), summarized and listed.

Prior and concomitant medications will be coded using the WHO_DRUG Dictionary, summarized, and listed.

Disposition, including receipt of doses, inclusion in study populations and reasons for dropout will be summarized and listed, and a CONSORT diagram will be prepared.

10.1.4 *Immunogenicity Data*

For an overview of primary and secondary endpoints, see Section 3.

For descriptive analyses, at each pre-and post-vaccination time point where neutralizing antibody titers are obtained:

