10.2 DETERMINATION OF SAMPLE SIZE

This study is designed to demonstrate the non-inferiority of different intervals of administration of nOPV2 (1-week and 2-week intervals) *versus* the standard 4-week interval based on the seroconversion rates of type 2 polio neutralizing antibodies 28 days following the second nOPV2 administration. Non-inferiority would be verified if the lower bound of the two-sided 95% CI around each difference (shorter interval minus standard interval) is greater than -10%.

The nOPV2 vaccine has recently been demonstrated to be non-inferior to Sabin-strain mOPV2 in a Phase 2 study⁸. In this Phase 2 study, among infants aged 18 weeks who had previously been vaccinated with bOPV and IPV, and using a 4-week interval between 2 doses, the cumulative seroconversion rates were near 100%, similar to the mOPV2 historical control group. A prior study of dosing intervals of 1, 2, and 4 weeks conducted

14 August 2021 (Version 1.0)

with mOPV2 in Bangladesh demonstrated seroresponse rates of 93.1%, 95.5% and 97.2% respectively, with lower confidence bounds of 88.3%, 91.3%, and 93.7%¹⁷.

This study will be conducted in the Dominican Republic, and it is not anticipated that immune response rates will be lower than those observed in the previous mOPV2 study. Therefore, with a conservative assumed cumulative 2-dose seroconversion rate of 85% in each group, 270 evaluable subjects per group are required to demonstrate non-inferiority of each of the shorter intervals to the standard interval, using margin 10%, two-sided Type I error rate of 5%, and requiring 90% power. This will be further increased to 300 per group to account for loss to follow-up or other loss from the evaluable population.

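### Read literally, Section 5.4 withholds dose 2 from an infant judged too ill with an acute severe febrile illness on the dosing day, even if the infant recovers within the +2 day window

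*Combined protocol and SAP*

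**What the plan says.** Section 5.4 opens its list with "The following AEs constitute absolute contraindications to further administration of the study vaccine". One item is "Acute severe febrile illness on the day of vaccination deemed by the Investigator to be a contraindication for vaccination". The section closes with "If any of these AEs occur during the study, the subject should not receive the second dose of vaccine", and adds that other study procedures may continue at the investigator's discretion. It has no deferral clause.

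Exclusion criterion 10 in Section 5.2 describes the same condition at enrolment, but adds that "the child can be included at a later time if within age window and all inclusion criteria are met".

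In the Time and Events Schedule, the dose-2 visit is Day 7 (Group A, Table 1), Day 14 (Group B, Table 2) or Day 28 (Group C, Table 3), each with a window of +2 days. Section 5.3 sends "vaccinations occurring out of window" to protocol deviation review; it does not name doses given inside the window.

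Section 10.1.1 limits the Per-Protocol (PP) Population to infants "who received all of the immunizations at the interval scheduled for the group to which they were allocated". It also adapts that population by time point, to "allow subjects to contribute data to PP analyses until such time as they become disqualified".

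**The concern.** The other items in Section 5.4 are mostly lasting reasons to stop: a related serious or grade 3 event, hypersensitivity, immunodeficiency, acute flaccid paralysis. The febrile-illness item is tied to a single day, yet it sits under the same absolute heading and the same closing sentence. Once the investigator has judged the illness contraindicating, the stated discretion covers other procedures and not dose 2.

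Protecting the randomised interval does not explain the bar inside the window, because the schedule already accepts dose 2 up to two days late.

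At stake are a few avoidable missed doses. Each such infant also has no post-dose-2 result in the PP Population, where immunogenicity is primarily analysed. The Day 0 and pre-dose-2 data still count, follow-up continues under Section 5.4, and IPV remains scheduled at Day 35, 42 or 56.

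**Working it through.** **1. The rules compared**

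| | Dose 1 (exclusion 10) | Dose 2 (Section 5.4) |
|---|---|---|
| Trigger | Acute severe febrile illness that day, judged contraindicating by the investigator | Same |
| Stated consequence | May be included later | Second dose not to be given |
| Time available | Remainder of the 6 to 8 week age range | +2 days, but no deferral clause |

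No other section permits dose 2 to be deferred after such an illness. Section 11.4 offers a temporary-stop code for recording the action taken, but no rule for resuming.

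**2. Do later visits still fit if dose 2 is given on the last window day?** (Tables 1 to 3)

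| | Group A | Group B | Group C |
|---|---|---|---|
| Last dose-2 day | 7 + 2 = 9 | 14 + 2 = 16 | 28 + 2 = 30 |
| 7-day contact | 9 + 7 = 16 | 16 + 7 = 23 | 30 + 7 = 37 |
| Contact window ends | 14 + 2 = 16 | 21 + 2 = 23 | 35 + 2 = 37 |
| 28-day serum | 9 + 28 = 37 | 16 + 28 = 44 | 30 + 28 = 58 |
| Serum window ends | 35 + 2 = 37 | 42 + 2 = 44 | 56 + 2 = 58 |

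Everything fits, with no slack. In Group A a Day 9 dose makes the interval 9/7 − 1 = 29% longer than nominal, which Table 1 already allows.

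**3. How many infants?** The documents give no rates, so these are assumptions: 0.5% to 2% of infants have a contraindicating illness on the dose-2 day, and 25% to 50% of those recover within two days.

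- Low end: 300 × 0.005 × 0.25 = 0.375 per group, about 1.1 of 900.
- High end: 300 × 0.02 × 0.50 = 3 per group, 9 of 900.

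**4. Effect on power.** Inputs from Section 10.2: 85% seroconversion in each group, margin 10%, two-sided 5% error, 90% power, and "270 evaluable subjects per group are required", raised to 300.

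The plan's figure first, by the normal approximation: n = (1.960 + 1.282)² × 2 × 0.85 × 0.15 / 0.10², which rounds up to 268 per group. This agrees closely with 270. The allowance is 300 − 270 = 30 per group, or 10%.

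Power = Φ(0.10 / √(2 × 0.85 × 0.15 / n) − 1.96):

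| Evaluable per group | Power |
|---|---|
| 300 | 92.9% |
| 297 (300 less 3) | 92.7% |
| 270 | 90.2% |
| 267 (270 less 3) | 89.9% |

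Even if the whole allowance were already spent on other losses, the high end costs 90.2 − 89.9 = 0.3 percentage points. If this were the only loss, power stays at 92.7%.

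**The case against.** The strongest reply is that the item can be read as barring vaccination on that day only. If the visit is moved within the window and the infant is well, there is arguably no febrile illness on the day of vaccination, and the temporary-stop code in Section 11.4 would suit such a delay. That reading is possible. Against it stand the absolute heading, the closing sentence and the absence of the clause that exclusion 10 carries. If both readings are open, sites in this multicenter trial may act differently, which is itself a reason to settle the wording.

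A second reply is that the rule may be deliberate. Dose 1 can be rescheduled within an age range, while dose 2 has two days. Not giving a live vaccine to a young infant who was severely ill a day or two earlier is a defensible caution. The documents neither state nor exclude this. Leaving recovery to the investigator's judgement preserves that caution.

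Third, the trigger is narrow: the illness must be acute, severe and judged contraindicating. A reader might infer that any fever on the visit day costs an infant dose 2; the text does not say so.

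Fourth, Section 10.2 provides for loss from the evaluable population, and these infants fall within that allowance. This stands in full. A reader might also infer a threat to the non-inferiority conclusion, or a loss that differs by group. The documents give no rate, overall or by group, to support either.

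**Conclusion.** The gap is real on the literal wording, and minor. Section 5.4 treats as permanent a condition that exclusion 10 treats as temporary, although the schedule leaves two days in which dose 2 could still be given. The likely effect is a handful of infants at most: 0.4 to 3 per group, resting entirely on the assumed illness and recovery rates. That is at most 3 of the 30 per group allowed for loss. The sample size stands and the primary conclusion is unaffected. The case for changing the text is to avoid unnecessary missed doses and lost post-dose-2 PP data, and to have all sites apply the same rule. It is worth considering but not essential.

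**What to change.** Move the febrile-illness item out of the absolute list in Section 5.4 and make it a temporary contraindication, as follows:

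- **Dosing:** once the investigator judges the illness resolved, dose 2 may be given up to Day 9 (Group A), Day 16 (Group B) or Day 30 (Group C), and counts as per protocol.
- **Other bars:** all other items in Section 5.4 still apply, including related SAEs, IMEs and grade 3 events.
- **Pre-dose-2 serum:** draw it once, on the actual dose-2 day before the dose. If it was already drawn on the nominal day, do not repeat it.
- **Later assessments:** hold the 7-day contact and take the 28-day serum 7 and 28 days after the actual dose, within the existing windows (latest Day 16, 23 or 37 for the contact; Day 37, 44 or 58 for the serum).
- **No recovery in time:** if the infant is still ill when the window closes, dose 2 is not given and follow-up continues as Section 5.4 now states.

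No deferral beyond +2 days is proposed, because the interval is the randomised treatment.

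The cost is an edit to one section and one return attendance, with reassessment before dosing, for each deferred infant. After a dose at +2 days the later visits have no slack, as is already true of any dose 2 given that late. Where serum was drawn on the nominal day, it precedes the dose by up to two days.
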